2.4 SCREENING AND BASELINE EVALUATIONS

Evaluations required at baseline can be omitted if obtained at screening within 1 week of Cycle 1 Day 1. The baseline (enrollment) EKG may be used as pre-infusion EKG on Cycle 1, Day 1. The baseline CT scan of the chest, abdomen, and pelvis can be omitted if obtained at screening within 16 days of Cycle 1 Day 1.

2.4.1 Imaging Studies

Every participant must have a CT scan of chest, abdomen and/or pelvis prior to receiving treatment. PET/CT alone is not sufficient. These tests are deemed medically indicated to establish baseline disease characteristics. This must be completed within 16 days prior to enrollment. Participants with CT contrast hypersensitivity in the presence of appropriate pre-medication may be followed by MRI with gadolinium per investigator-approval. A contrast CT or MRI of brain may be requested if a participant has advanced breast cancer or has symptoms or physical examination findings that suggest a risk of brain metastases. In some participants, an MRI, PET, bone scans, or ultrasound may be appropriate to include in disease monitoring and may be included in addition to the baseline CT scan.

2.4.2 An EKG should be obtained within 1 week prior to enrollment.

2.4.3 Laboratory Evaluations [baseline is to be obtained within 1 week prior to enrollment].

- Hematological profile: CBC with differential and platelet count, PT/INR/PTT
- Biochemical profile:
 - Screening – Bilirubin, AST, ALT, creatinine or creatinine clearance
 - Baseline - 14 comprehensive metabolic panel (sodium, potassium, chloride, carbon dioxide, BUN, creatinine or creatinine clearance, glucose, AST, ALT, bilirubin, calcium, total protein, albumin, alkaline phosphatase), magnesium, urinalysis

CC Protocol #: 14-C-0156

Abbreviated Title: LY Chk1/2 Inhibitor

Amendment Version Date: 12/02/2020

- CA125 will be followed on all ovarian cancer and participants in whom it has been shown to be abnormal. CA125 will not be used in any participants for disease assessment decisions.
- Serum beta-hCG or urine pregnancy test in women of childbearing potential.

3 STUDY IMPLEMENTATION

3.1 STUDY DESIGN

This is an open label, non-randomized phase II pilot trial to examine activity of LY2606368 in participants in 6 independent cohorts:

- 1) Women with BRCA mutant breast or ovarian cancer
- 2) HGSOC at low genetic risk
- 3) TNBC at low genetic risk
- 4) mCRPC with or without BRCA mutation: Effective with Amendment I (version date 4/24/2017), Cohort 4 was closed to accrual.
- 5) Recurrent platinum-resistant HGSOC at low genetic risk
- 6) Recurrent platinum-resistant HGSOC at low genetic risk without biopsiable disease

Participants will be evaluated at baseline and prior to each cycle by history and physical examination (H&P). Laboratory studies will be performed prior to each drug administration. In cohorts 1 – 3, 5 and 6, participants will be evaluated every two cycles by imaging studies using RECIST criteria (CT scan or other as appropriate). In the mCRPC cohort, participants will be evaluated by imaging studies using RECIST criteria (CT scan and other imaging as appropriate) and technetium 99 bone scan³⁶ every 3 cycles. All participants in this cohort will have baseline CT and technetium 99 bone scan imaging. As per the Prostate Cancer Clinical Trials Working Group 2 recommendations, every effort should be made to keep participants on treatment with LY2606368 for at least 12 weeks³⁶ and thus for the purposes of this cohort, participants should be evaluated every 3 cycles. Effective with Amendment I (version date 4/24/2017), mCRPC cohort 4 was closed to accrual.

Participant adherence to drug treatment and reporting of adverse effects will be reviewed by history.

LY2606368 is administered intravenously once every 14-days in each 28-day cycle. Administration of LY2606368 may be delayed up to 7 days due to holidays, inclement weather, conflicts, or similar reasons. The timing of subsequent administrations is then adjusted to maintain a 14 days-interval. For safety reasons, LY2606368 may not be administered with less than a 14-days interval.

CC Protocol #: 14-C-0156
Abbreviated Title: LY Chk1/2 Inhibitor
Amendment Version Date: 12/02/2020

Table 4. Dose Levels of LY2606368

Dose Level (DL)	LY2606368 IV q2w (mg/m ²)
Starting Dose DL1	105
DL-1	80
DL-2	60

3.2 DRUG ADMINISTRATION

See [Study Schema](#):

The RP2 dose of 105 mg/m² LY2606368 administered by IV over 1 hour (**+15 minutes**) once every 14 days will be used. Administration of LY2606368 may be delayed up to 7 days due to holidays, inclement weather, conflicts, or similar reasons. The timing of subsequent administrations is then adjusted to maintain a 14 days-interval. For safety reasons, LY2606368 may not be administered with less than a 14-days interval.

Participants should avoid taking concomitant medications that are known or suspected to cause prolonged QTc or Torsades de Pointes ([Appendix B](#)) 12 hours before through 12 hours after administration of LY2606368 and, if possible, alternative agents should be considered.

Participants will continue therapy until documentation of progressive disease, limiting toxicity ([3.3](#)), intercurrent medical issues, or participant withdrawal. Participants with CR will discontinue therapy two cycles past a radiographically confirmed CR (see [6.2.4](#) for guidance), and will then be followed actively in clinic every 4 weeks with reassessment noninvasive imaging on an every 12 week schedule until progression or withdrawal. Participants with signs or symptoms of clinical progression may be imaged earlier in order to provide optimal care.

Palliative radiation therapy may be considered for symptom and/or pain control in consultation with Radiation Oncology, only for those who continue to have clinical benefit from LY2606368 treatment at the PI's discretion (see section [14.1.2](#) for guidance of concurrent radiation therapy and LY2606368).

Participants will be contacted over the phone or assessed in person at least once weekly during the first cycle of treatment. Subsequent follow up will be at least monthly, with the start of each new cycle, and then during follow up according to the defined schedule (see [3.4: Study Calendar](#)).

Pre-cycle and off-treatment AE assessments will be done at a scheduled clinic visit. Off-study assessments will be performed within 30 days of stopping study treatment over the phone or at a clinic visit.

CC Protocol #: 14-C-0156
 Abbreviated Title: LY Chk1/2 Inhibitor
 Amendment Version Date: 12/02/2020

3.3 DOSE MODIFICATIONS

See [Table 4](#) Dose Levels.

Table 5: Treatment modifications of LY2606368 for hematologic toxicities *

Grade	Occurrence	Immediate Action	Resumption of Therapy
1	All	None	No interruption
2	All	None	No change in dose, but initiate appropriate medical therapy
3	1 st **	Hold therapy until grade ≤ 2	Initiate appropriate medical therapy and no change in dose upon re-initiation if recovers to grade 2 or better within 3 weeks
	2nd**	Hold therapy until grade ≤ 2	Initiate appropriate medical therapy and then reduce LY2606368 to the next lower dose level upon re-initiation
4	All **	Hold therapy until grade ≤ 2	Initiate appropriate medical therapy and then reduce to the next lower dose level upon re-initiation

* For adverse events that are possible, probable, or definitely attributable to LY2606368 alone (attributions 3-5).

** Any event of temporary (≤ 7 days) afebrile neutropenia (grade 3 or grade 4) will not require dose reduction or discontinuation of treatment.

** Grade 3 or 4 thrombocytopenia > 7 days or any thrombocytopenia requiring platelet transfusion for bleeding will result in dose reduction to the next lower dose level (see [3.3.1.2](#)).

** If the first event of grade 3 anemia is refractory to red cell transfusion and growth factor support within 3 weeks then LY2606368 should be dose reduced to the next lower dose level (see [3.3.1.3](#)).

** If no resolution occurs within the 3-week period, the study drug will be discontinued.

3.3.1 Hematologic Toxicity

Hold LY2606368 for participants with grade 3 or 4 hematologic toxicities until they recover to grade 2 or better. The participants at a high-risk for bleeding; e.g., concurrent use of anti-coagulation, may hold LY2606368 until platelets recover to grade 1 or better. Blood counts will be repeated every other day until resolution to grade 2 or better.

CC Protocol #: 14-C-0156

Abbreviated Title: LY Chk1/2 Inhibitor

Amendment Version Date: 12/02/2020

3.3.1.1 Neutropenia:

- Prophylactic and/or therapeutic growth factor support will be given following the ASCO practice guidelines³².
- Participants who experience grade 3 or 4 neutropenia or fever during neutropenia and are not receiving growth factor support can be supplemented with filgrastim 5 mcg/kg/day until ANC is greater than 3,000/ml, or pegfilgrastim 6mg at the discretion of the team.
- If recurrent grade 3 or 4 neutropenia (> 7 days) is refractory to growth factor support, then LY2606368 should be dose reduced to the next lower dose level.
- A subsequent event of grade 4 neutropenia (> 7 days) or fever during neutropenia, while on therapeutic or prophylactic filgrastim growth factor support, will necessitate discontinuation of a study drug.
- Participants with ANC \leq 1500/mL on day 1 of a cycle may receive filgrastim 5 mcg/kg for a period of 3-5 days or pegfilgrastim 6mg to avoid treatment delays and risk of dose reduction, if they did not receive growth factor support in the immediately preceding cycle.
- Prophylactic antibiotics may be considered for use in participants that have experienced febrile neutropenia on the study or participants deemed at higher risk for febrile neutropenia by the investigators.

3.3.1.2 Thrombocytopenia:

- Asymptomatic grade 3 or 4 thrombocytopenia lasting \leq 7 days will not result in drug discontinuation.
- Grade 3 or 4 thrombocytopenia > 7 days or any thrombocytopenia requiring platelet transfusion for bleeding will result in dose reduction to the next lower dose level.
- The participants at a high-risk bleeding, e.g., concurrent use of anti-coagulation may hold LY2606368 until platelets recover to grade 1 or better (\geq 75,000/mm³).

3.3.1.3 Anemia:

- The first line response to symptomatic anemia is introduction of red cells, and consideration of growth factor support if participants require recurrent red cells transfusion.
- Symptomatic anemia should be treated with red blood cell transfusion and is recommended if the hemoglobin falls below 8 g/dL.
- The initiation of erythropoietic therapy for the management of chemotherapy-induced anemia follows the American Society of Hematology/ASCO clinical practice guidelines (<http://www.asco.org>).
- If grade 3/4 anemia is refractory to red cell transfusion and growth factor support within 3 weeks, then LY2606368 should be dose reduced to the next lower dose level.

Table 6: Treatment modifications of LY2606368 for non-hematologic toxicities *

Grade	Occurrence	Immediate Action	Resumption of Therapy
1	All	None	No interruption

CC Protocol #: 14-C-0156

Abbreviated Title: LY Chk1/2 Inhibitor

Amendment Version Date: 12/02/2020

Grade	Occurrence	Immediate Action	Resumption of Therapy
2	All	Hold therapy until grade ≤ 1	No change in dose, but initiate appropriate medical therapy
3	1 st **	Hold therapy until grade ≤ 1	No change in dose, but initiate appropriate medical therapy
	2nd**	Hold therapy until grade ≤ 1	Initiate appropriate medical therapy and then reduce LY2606368* to the next lower dose level upon re-initiation
4	1 st	Discontinue therapy	

*For adverse events that are possibly, probably, or definitely attributable to LY2606368 alone (attributions 3-5)

**Treatment will be discontinued if participants require the second dose reduction (see [3.3.1.1](#)) see [3.3.3](#) below for exemptions of **

Drug will be reinitiated upon resolution of toxicity to grade 1 or better or as qualified below. Delay of treatment due to recovery may not persist longer than 3 weeks. Once a participant has a dose reduction for toxicity, the dose will not be increased back to the starting dose. Treatment will be discontinued if participants require the second dose reduction due to the occurrence of the same events.

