Preliminary results from 32 heavily pretreated HGSOC patients have been presented at the European Society of Medical Oncology meeting in October 2016, including 7 patients in Cohort 1 (patients with a documented *BRCA* mutation) and 25 patients in Cohort 2 (patients with a negative family history of hereditary breast ovarian cancer syndrome, or negative germline *BRCA* mutation test). Transient grade 4 neutropenia was observed in 69% of patients and resolved to less than or equal to grade 2 within 8 days after onset. Two patients (6%) had febrile neutropenia. Only one patient had dose reduced to 80mg/m². Other toxicities included decreased white blood cell count (78%), anemia (66%), and decreased platelet count (34%). Nonhematologic AEs were generally mild and included fatigue, nausea, vomiting, and diarrhea (9% each). One patient experienced Grade 3 diarrhea and vomiting during infusion.

Among 20 evaluable patients in HGSOC (Cohort 2), there were 7 confirmed PRs, for an ORR of 7 of 20 (35%). Patients had a median of 5 previous therapies (range: 1 to 13). Of the 20 evaluable patients, 15 had platinum-resistant or platinum-refractory disease. Five of 15 patients had a PR for an ORR of 33%. The interim median duration of response is 6 months (3+ to 9 months). The numbers of previous therapies for the responders were 2, 4, 5, 6, and 13. An additional 5 patients with platinum-resistant or platinum-refractory disease had SD \geq 4 months for an overall clinical benefit rate of 66% (10 of 15). Six of 10 patients who had a PR or SD \geq 4 months had received previous bevacizumab. Notably, an expected RR for this patient population with existing agents is approximately 15% (unpublished meta-analysis conducted by Eli Lilly in 2 lines+ ovarian cancer). None of the 6 evaluable patients in Cohort 1 achieved CR or PR, but 4 (67%) achieved SD lasting at least 4 months, for a DCR of 67%. However, our *BRCA* mutant patient cohort, in which all patients received prior PARP inhibitors, did not show response to LY2606368, suggesting CHK1/2 inhibition alone may not reverse the observed PARP inhibitor resistance. **Figure 8** presents a plot of best responses for target lesions by patient, among patients treated with LY2606368.

CC Protocol #: 14-C-0156
 Abbreviated Title: LY Chk1/2 Inhibitor
 Amendment Version Date: 12/02/2020

Abbreviation: *gBRCAm* = germline *BRCA* mutated.

Figure 8. Best response for target lesions by patient, among patients treated with LY2606368

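### The hematologic dose-modification rules prescribe different actions for the same event: reduction or discontinuation for refractory grade 3 anemia, and likewise for prolonged or febrile neutropenia on filgrastim

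*Combined protocol and SAP*

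**What the plan says.** **Table 5 (Section 3.3).** For grade 4 hematologic toxicity, at all occurrences, drug is held until grade 2 or better and then: "Initiate appropriate medical therapy and then reduce to the next lower dose level upon re-initiation". A first grade 3 event restarts at the same dose if it recovers within 3 weeks; a second is a reduction. The neutropenia exemption is: "Any event of temporary (≤ 7 days) afebrile neutropenia (grade 3 or grade 4) will not require dose reduction or discontinuation of treatment".

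**Table 5 footnotes on anemia and time limit.** One footnote calls for reduction: "If the first event of grade 3 anemia is refractory to red cell transfusion and growth factor support within 3 weeks". The last footnote is a stopping rule: "If no resolution occurs within the 3-week period, the study drug will be discontinued".

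**Section 3.3.1, opening paragraph.** Drug is held for grade 3 or 4 hematologic toxicity until recovery to grade 2 or better.

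**Section 3.3.1.1 (neutropenia).** The third bullet reduces the dose by one level on this condition: "If recurrent grade 3 or 4 neutropenia (> 7 days) is refractory to growth factor support". The fourth requires discontinuation for: "A subsequent event of grade 4 neutropenia (> 7 days) or fever during neutropenia, while on therapeutic or prophylactic filgrastim growth factor support".

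**Section 3.3.1.3 (anemia).** The dose is reduced if grade 3 or 4 anemia is refractory to transfusion and growth factor within 3 weeks.

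**Paragraph after Table 6 (the non-hematologic table).** A delay for recovery may not exceed 3 weeks, and treatment stops if a second reduction is needed for the same event. A Table 6 footnote on the second reduction cross-refers to Section 3.3.1.1.

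**The concern.** Section 1.2 names neutropenia as the drug's most frequent toxicity and reports grade 3/4 anemia in 19% of phase 1 patients, so these rules will be used. Where two passages give different actions for one event, two investigators who both follow the protocol can treat the same participant differently, one lowering the dose and the other stopping the drug. That is first a matter of participant safety and consistent conduct. I found no passage that says whether the table or the text prevails. The removal criteria in Section 3.6.1 do not help: for unacceptable adverse events they refer to Section 3.3.3, which covers non-hematologic toxicity only.

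**Working it through.** No arithmetic is at issue. I read the action for each event from each place and set the results side by side.

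| Event | Table 5 and footnotes | Section 3.3.1.1 or 3.3.1.3 |
|---|---|---|
| A. First grade 3 anemia, refractory, unresolved at 3 weeks | Anemia footnote: reduce. Last footnote: discontinue | Reduce |
| B. Grade 4 anemia that responds to support | Reduce | No reduction specified |
| C. Subsequent grade 4 neutropenia over 7 days on filgrastim | Reduce | Discontinue |
| D. Fever during grade 4 neutropenia on filgrastim | Reduce | Discontinue, if *subsequent* does not limit the fever limb or if the event is a later one |
| E. Second grade 3 neutropenia, febrile, on filgrastim | Reduce | Discontinue |
| F. First grade 4 neutropenia over 7 days | Reduce | Silent |

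**Event A.** A reduced dose can be given only at a restart. Section 3.3.1 bars a restart before grade 2. The last Table 5 footnote stops the drug if the event is unresolved at 3 weeks, and the paragraph after Table 6 caps delay at 3 weeks. A participant still at grade 3 after 3 weeks therefore has no route to the reduced dose that the anemia footnote and Section 3.3.1.3 prescribe.

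**Event B.** Table 5 attaches no refractory condition to grade 4; Section 3.3.1.3 does. Section 3.3.1.3 does not say that a responsive grade 4 anemia keeps its dose, so this is a difference in stated conditions.

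**Event C.** The fourth bullet does not say what the event is subsequent to, so I tried both readings.

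1. *After any earlier episode.* Suppose the earlier episode was afebrile and lasted 7 days or less. The Table 5 exemption meant no reduction. The next episode, over 7 days on filgrastim, is then a first reduction under Table 5. The second-reduction rule is not triggered, and the fourth bullet discontinues. The passages conflict.
2. *After a reduction under the third bullet.* The two bullets then form a sequence. Table 5 would reduce again where the fourth bullet discontinues. The second-reduction rule brings them into line, but only if it applies to hematologic events, and it is printed under the non-hematologic table.

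On neither reading is the case settled by the text.

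**Events D and E.** Table 5 exempts only afebrile events, so febrile grade 4 neutropenia stays in the grade 4 row (reduce) and a second febrile grade 3 event in the second-occurrence row (reduce). The fourth bullet names fever during neutropenia without a grade and discontinues. Whether *subsequent* also governs the fever limb is unclear, so it is open whether a first febrile episode on prophylactic filgrastim means stopping.

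**Event F.** The third bullet says when to reduce. It does not say that reduction is confined to that case.

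**Numbers available (Section 1.2).** Phase 1: grade 4 neutropenia was often under 5 days; febrile neutropenia in 11%. First 32 HGSOC patients in this trial: febrile neutropenia in 2 (2/32 = 6%); reduction to 80 mg/m² in 1 (1/32 = 3%). Neither source gives the number with grade 4 neutropenia over 7 days or with refractory anemia.

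**The case against.** The best defense is that most of this can be read together. For a first prolonged episode, a passage that speaks and one that is silent can both be followed; that is right, and event F is no explicit contradiction. The third and fourth neutropenia bullets can be read as reduce, then stop. The second-reduction rule would then make Table 5 reach the same end, and the Table 6 footnote's cross-reference to Section 3.3.1.1 suggests that the rule was meant to reach neutropenia. This removes part of the repeat-episode conflict, but not where no earlier reduction was made, and only if the rule's reach is accepted. For anemia, one footnote might cover cases judged refractory that still recover in time, and the other those that do not. The wording does not draw that line.

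Three stronger readings are tempting and not supported. A reader might infer that Section 3.3.1.1 forbids reduction at a first prolonged episode; it says if, not only if. A reader might take the interim figure ("Transient grade 4 neutropenia was observed in 69% of patients") as the share affected. Those events were described as transient, and their resolution within 8 days is time to grade 2 or better, which does not show how many lasted over 7 days. A reader might also infer damage to the interpretation of PFI or dose intensity. Section 10 plans no dose-intensity analysis, Section 6.1 requires doses and reasons for modification to be recorded, and nothing in the documents shows an effect on PFI.

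**Conclusion.** The point holds for specific events. The anemia conflict is the clearest: the reduction and discontinuation footnotes in Table 5 overlap, and the hold and delay limits leave no route to the reduced dose. The neutropenia conflict on filgrastim is real where no earlier reduction was made, and otherwise turns on whether the second-reduction rule covers hematologic events. The first prolonged episode is a difference by implication and should be described as such. The number of participants affected cannot be derived; the interim experience suggests a small subset. The conclusion rests on the wording alone and implies no view on which action is clinically right. It should be corrected because it bears on participant safety. No consequence for the efficacy analysis is claimed.

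**What to change.** Reconcile Table 5, its footnotes, Sections 3.3.1.1 and 3.3.1.3 and the second-reduction rule after Table 6, so that each event has one stated action, chosen by the investigators. The events to cover are:

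- anemia: grade 3 or 4, responsive or refractory, resolved or unresolved at 3 weeks;
- neutropenia: first or later episode, up to or over 7 days, febrile or afebrile, on or off growth factor, with or without an earlier reduction.

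The amendment should also state whether the table or the text governs if they differ, whether the second-reduction rule and the 3-week delay limit after Table 6 apply to hematologic events, what *subsequent* refers to in the fourth neutropenia bullet, and whether it limits the fever limb. The cost is amendment wording; sample size, endpoints and analyses do not change.

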3.3.2 QTc Prolongation

On study monitoring:

- ECGs will be performed before and at the end of infusion of each LY2606368 (within 30min +/- 20min), every two weeks x2, every 4 weeks x1, then every 3 months.
- For a single QTcF value of >500 ms, LY2606368 must be held. Electrolytes will be corrected and ECGs followed at least once per week, until QTcF falls below 480 ms.
- When drug is restarted after the QTcF prolongation has resolved within 3 weeks, ECGs (and electrolytes) should be followed every 2 weeks x2, every 4 weeks x1, then every 3 months.
- Serum potassium levels should be maintained ≥ 3.6 mEq/L, and serum magnesium and serum calcium should be kept within normal range to reduce the risk of QTcF prolongation. Some ovarian cancer participants who have had exposure to cis- and carboplatin may have persistent hypomagnesemia or hypokalemia despite replacement to

CC Protocol #: 14-C-0156

Abbreviated Title: LY Chk1/2 Inhibitor

Amendment Version Date: 12/02/2020

the point of induction of diarrhea (if not within a normal range). Such participants will be closely monitored during the treatment, with IV potassium or additional dose of magnesium repletion.

